Repetitive Transcranial Magnetic Stimulation (rTMS) in Fibromyalgia

NCT number: **NCT03909009**

Date: **14.03.2019**

Objectives

Fibromyalgia syndrome (FMS) is a chronic pain condition characterized by widespread pain, stiffness, overwhelming fatigue, sleep disturbance, alteration in mood, cognitive dysfunction (fibrofog) and impaired quality of life and daily function (1,2). FMS is present in as much as 0.2% to 6.6% of the general population and is more common in women than in men (3). It has substantial impacts on quality of life, physical functioning and social-occupational productivity therefore financial costs are an economic burden to these patients (4). The pathophysiology of this syndrome is still unknown but genetic predisposition, hypothalamic-pituitary-adrenal axis dysfunction, environmental factors, autonomous dysfunction, metabolic factors, neuropathies and neuromodulation all being considered to be involved in the onset and course of the disease (2,5). As we know today, the most acceptable theory is the central sensitization that includes altered pain processing based on peripheral and central nervous system influences (5,6).

The purpose of FMS management is to reduce pain, improve sleep and restore physical, emotional and mental function, thereby improving overall quality of life but there is no gold standard treatment method due to the difficulty of the diagnosis of the disease as well as the unknown pathophysiology (2,7). High quality evidence are supporting multidisciplinary approach that include nonpharmacological therapies (education, exercise, cognitive behavioral therapy, physical-therapy agents, acupuncture, multicomponent treatments) and pharmacological therapies (tricyclics, serotonin norepinephrine reuptake inhibitors, and gabapentinoids) to achieve optimal management results (7-9). Recently, a growing number of studies are performed on modulation of

central pain pathways of FMS. The promising treatment option in this regard is seen as neuromodulation techniques such as transcranial magnetic stimulation (TMS) (10,11).

Repetitive transcranial magnetic stimulation (rTMS) is a safe and non-invasive method of stimulating neurons in the cerebral cortex. It is used to induce changes in brain activity that can produce after-effects on the brain (12,13). rTMS modulates cortical plasticity, which is called the functional rearrangement of connections between neurons and neuronal features (12,13). It is generally assumed that rTMS-induced effects may closely relate to synaptic plasticity, such as long-term potentiation (LTP) or depression (LTD) (13,14). An after-effect induced by rTMS depends on stimulation frequency. High-frequency rTMS at 5 Hz or higher transiently increases cortical excitability (i.e. LTP-like), while stimulation at 1 Hz decreases cortical excitability (LTD-like) (14). rTMS also affects brain activities related to pain modulation and processing. Therefore, its use in pain syndromes is increasing (15,16). Additionally, rTMS offers potential for clinical application in a variety of neurological, psychiatric diseases (e.g. stroke, Parkinson, dementia, depression) (16-18). Also recently, the success of these treatments is enhanced by using neuronavigation systems that accurately position the coil on a target and keep the coil in the correct place during the session (19).

Although there are many randomized clinical trials and meta-analysis revealing beneficial effects of rTMS in FMS, there is no consensus regarding the exact efficacy, neither on the optimal parameters of stimulation. Studies have generally focused on high frequency stimulation of the left primary motor cortex (M1) or left dorsolateral prefrontal cortex (DLPFC). In recent meta-analysis, few randomized controlled, double-blind studies were evaluated and these studies mainly investigated pain, quality of life, and mood in FMS. Klinck et al., reported that there was no significant difference between

sham or active rTMS for reducing pain or depression but active rTMS was associated with a significant improvement on quality of life (11). Saltychev et al. revealed moderate evidence that rTMS is not more effective than sham in reducing the severity of pain in FMS (20). Hou et al. suggested that M1 stimulation may be better in pain reduction and the DLPFC may be better in depression improvement (10). On contrary to this study, recently Lefaucheur et al. reported that high frequency-rTMS of the left DLPFC is more efficacious on pain, while high frequency -rTMS of the left M1 is more efficacious on the quality of life (21). In addition, there are very few studies investigating the effect of TMS treatment on cognitive dysfunction, which is an important problem in FMS (22). It is clear that there is still a need for further studies on the exact clinical effects of rTMS treatment in FMS.

Therefore, this study aimed to evaluate the effectiveness of 10 Hz neuronavigated rTMS to the left DLPFC on pain, stiffness, fatigue, depression/anxiety, quality of life and cognitive functions in FMS.

Methods

Participants

Participants were recruited from Physical Medicine and Rehabilitation (PMR) outpatient clinics of a university hospital. Twenty patients (mean ages: 45.25 ± 9.08 years, range 29 to 64 years; 20 females) with FMS who met the following inclusion criteria were included in the study: (1) adults (age between 18-65 years); (2) diagnosis of FMS according to 2016 Fibromyalgia diagnostic criteria; (3) the mean pain intensity is VAS $\geq 4 / 10$; (4) stable treatment for at least last 3 months. Patients were excluded: if they had a clinical condition to be contraindicated for TMS (e.g. metallic implant, cardiac pace, pregnancy, lactation, epilepsy, head trauma, history of cranial operation); significant medical or psychiatric illness including malignancy, major depression, personality disorder, history of substance or alcohol abuse; major orthopedic/ neurological problems that limit daily life activities; pregnancy/breastfeeding; concomitant inflammatory rheumatic diseases, autoimmune diseases or other painful disorders and patients who have received TMS treatment before.

Study design and ethics

This is a single-center, prospective, randomized, double-blind, sham-controlled study in two-arm parallel-group design. Participants were informed about the study and provided written informed consents. The protocol was performed in accordance with the ethical standards laid down in the 1964 Declaration of Helsinki and approved by the local Research Ethics Committee (Approval number: 14.03.2019/25). This study was registered on www.clinicaltrials.gov with ID NCT03909009.

Demographics

At baseline, demographic information including age, gender, weight, height, body mass index (BMI), dominant side, marital status, education level, occupation, disease duration, additional diseases, smoking and alcohol use, drugs used for FMS treatment were questioned.

Randomization and blinding

Randomization was performed using computer-generated block randomization with 1:1 allocation between the active rTMS group (Group A) and the sham-control group (Group B) by an independent researcher not involved in the rTMS treatment sessions, patient selection or clinical evaluations. Two different researchers conducted other parts of this double-blind study. One of the researchers performed patient selection and interventions. The second researcher was blinded about the distribution of groups, patient selection and interventions. The blind investigator performed patient evaluations at the beginning of treatment, at the end of the 2nd and 6th weeks. The patients did not know which group they were in during the study.

Outcome assessment and data collection

After recording general demographic data clinical assessments were performed. All clinical outcome measures were assessed by an experienced researcher who was familiarized with the scales and tests used in this study and who was blinded of the group assignment. The clinical assessments consisted of six main sections: (1) Pain severity (VAS-pain) (2) Stiffness severity (VAS-stiffness) (3) Fibromyalgia Impact Questionnaire (FIQ) (4) Fatigue Severity Scale (FSS) (5) Hospital Depression Anxiety Scale (HADS) (6) Addenbrook Cognitive Examination - revised version (ACE-R)

Primary clinical outcome measure included VAS-pain (at the end of the 2nd week) whereas secondary outcome measures included FIQ and VAS-pain scores at the end of the 6th week.

Visual analog scale: Pain severity and stiffness severity were evaluated with VAS. VAS is a psychometric measuring instrument designed to document the severity of disease-related symptoms. In this study, the severity of the pain and stiffness experienced at rest were assessed on a 10cm VAS (Total score: 0-10)(Higher scores mean a worse outcome) (0=no pain/stiffness, 10=severe pain/stiffness) at baseline, at 2nd week and at the end of treatment (6th week) (23).

Fibromyalgia Impact Questionnaire (FIQ): Functional health status and quality of life of the participants were assessed with the FIQ, which measures 10 different features (physical functioning, missed days of work, depression, anxiety, feeling good, morning tiredness, pain, stiffness, fatigue, and well-being over the past week). The total FIQ score is 0-80 points. High scores indicate low functionality level. In our study, FIQ was evaluated at baseline, at the end of the 2nd and 6th week (24).

Fatigue Severity Scale (FSS): Severity of fatigue was evaluated with FSS, a 9-item self-report questionnaire scale. Each item of this scale consists of statements that are scored on a seven-point Likert type scale ranging from 1 to 7. Total FSS score is calculated as mean value of the nine items. Higher scores indicate higher fatigue severity (Total score range: 1-7). FSS was assessed at baseline, at the end of the 2nd and 6th week (25).

Hospital Anxiety and Depression Scale (HADS): HADS is an assessment tool developed to identify the risk of anxiety and depression and measure its level and change of severity. Its subscales are anxiety and depression. It contains 14 questions in total, including 7 (odd numbers) measuring anxiety and 7 (even numbers) measuring

depression. The lowest and highest total score that a person can obtain from this scale are 0 and 42, respectively. High scores are associated with a worse psychiatric condition. HADS was evaluated at baseline and 6th week of study (26).

Addenbrook Cognitive Examination Revised (ACE-R): Addenbrook Cognitive Examination-Revised is a brief cognitive test that consists of 5 basic sections: attention and orientation, memory, verbal fluency, language and visual-spatial abilities. Total score that can be obtained is 0-100. Higher scores are associated with a better cognitive state. ACE-R is considered useful in discriminating cognitively normal subjects from patients with mild cognitive impairment. ACE-R was assessed at baseline and 6th week of our study (27).

Interventions

Twenty patients were randomized into two groups. After randomization, group A received total 14 sessions of rTMS, 10 sessions daily (5 days/week, 2 weeks) and 4 sessions weekly (1 day/week, 4 weeks). Group B received sham treatment in the same sessions and time.

Neuronavigated repetitive transcranial magnetic stimulation: Brain images for participants were performed on a 1.5T magnetic resonance scanner (GE Sigma HDxt, General Electric Medical Systems, Milwaukee, WI, USA) using an eight-channel head coil. Magnetic resonance imaging (MRI) scans of each participant's brain were imported to the 3D guided neuronavigation device (NeNa-Neural navigator, The BrainTRAK™, Brain Science Tools BV, Utrecht, Netherlands). Then, we performed brain segmentation and the creation of stimulation target. The location of the left DLPFC was determined by an experienced researcher in accordance with the literature (28). These information were saved and used to target the left-DLPFC in the future sessions. The position of the TMS

coil and the patient's head was tracked using the BrainTRAKTM, a magnetic position tracking device built into the Neural Navigator.

A Neuro-MS/D TMS device (Neurosoft, Russia) with a figure-of eight coil was used for rTMS. The participants were seated in a comfortable chair with headrest and armrests, and were told to rest both hands and upper limbs on top of their thighs. At the beginning of each session, the resting motor threshold (RMT) of each participant was determined using Neuro-MEP-Micro 2-channel Electromyogram (EMG) (Neurosoft, Russia) device. RMT was defined as the minimum stimulation intensity to evoke an MEP greater than 50 μ V in at least 5 of 10 single-pulse TMS trials applied to the left primary motor cortex (M1). EMG signals were recorded from electrodes placed over the first dorsal interosseous muscle of the right hand, with a circular ground electrode placed over the wrist. rTMS therapy was applied under the guide of neuronavigation with the following parameters: target-left DLPFC, with the %90 of the RMT, 10 Hz stimulation for 5 seconds intervals (on) with 25 seconds inter-train intervals (off), 15 minutes, 1500 pulses. The stimulation parameters of the study protocol are within the safety limits recommended for rTMS (29). For sham stimulation, probe localization was performed as in the active group but probe reversely positioned and during sham stimulation, patients heard a sound similar to the sound heard by those receiving the active treatment. Moreover, all patients were rTMS-naive, so they could not recognize the sham or active treatment techniques.

Sample size

Sample size calculation was performed with G*Power software (G*Power, version 3.1.9.2, Germany). A priori sample size based on the work of Tekin et al. (30) was calculated on the basis of changes in pain scores (VAS) evaluated before and after the

treatment. It was determined that at least 5, total 10 patients in each group should be included in the study according to 80% power, 5% margin of error and 1.73 effect size. Considering the statistical methods and the drop of patients from the study, the sample size was planned as at least 10 patients in each group and at least 20 patients in total.

Statistical analysis

Database management and statistical analyses were performed by an independent researcher. The statistical analysis was performed by SPSS Statistics 22.0 (IBM Corp., Armonk, New York, ABD) software. As the descriptive statistics, the number of units (n), percent (%), mean \pm standard deviation ($\bar{x} \pm ss$), median [IQR (interquartile range)] values were given. Distributions of continuous variables were evaluated using the Shapiro-Wilk test and Q-Q plots. Pearson chi-square test, Fisher's Exact test, and independent samples t-test were performed to determine differences between the demographic and clinical characteristic of the groups. Wilcoxon's signed-rank test and Mann-Whitney U-test were used to determine differences within and between the groups' baseline, 2nd or 6th week outcome parameters. If the two groups met the assumptions in terms of pain, stiffness, FIQ, and FSS variables measured at three different times, they were compared using bidirectional (treatment method \times time) variance analysis in repeated measurements. The variables examined in the 95% confidence level and P values less than 0.05 were considered significant.

Ethics Committee Approval

Author declared that the research was conducted according to the principles of the World Medical Association Declaration of Helsinki “Ethical Principles for Medical Research Involving Human Subjects”, (amended in October 2013).

University local Research Ethics Committee Approval number: 14.03.2019/25

Informed Consent

Written informed consent was obtained from the patients who participated in this study

Declaration of conflicting interests

The authors declared no conflicts of interest with respect to the authorship and/or publication of this article.

Funding

This work was supported by Izmir Katip Çelebi University Scientific Research Project fund.

Acknowledgement

None

References

1. Clauw DJ. Fibromyalgia: a clinical review. *JAMA* 2014;311:1547-55.
3. Marques AP, Santo ASDE, Berssaneti AA, Matsutani LA, Yuan SLK. Prevalence of fibromyalgia: literature review update. *Rev Bras Reumatol Engl Ed* 2017;57:356-63.

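### The primary outcome, week-2 VAS-pain, has no single named analysis and no baseline-adjusted between-group comparison at that visit

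*Combined protocol and SAP*

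**What the plan says.** Under Outcome assessment and data collection, the primary outcome is a score at one visit: "Primary clinical outcome measure included VAS-pain (at the end of the 2nd week". It is not defined as a change from baseline. VAS-pain is recorded at baseline, week 2 and week 6, so a baseline value exists for each patient.

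The Statistical analysis section offers two routes:

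- Rank tests: "Wilcoxon's signed-rank test and Mann-Whitney U-test were used to determine differences within and between the groups' baseline, 2nd or 6th week outcome parameters".
- A treatment × time "variance analysis in repeated measurements", which applies on a condition: "If the two groups met the assumptions in terms of pain, stiffness, FIQ, and FSS variables measured at three different times".

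Neither route is designated primary. The section names no baseline covariate, between-group test of change, week-2 contrast, or between-group estimate with a confidence interval.

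Two further outcomes have only baseline and week-6 values and are not in the ANOVA list: "HADS was evaluated at baseline and 6th week of study" and "ACE-R was assessed at baseline and 6th week of our study". Between groups, they have the Mann-Whitney comparison alone.

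The Sample size section works on before-after change in VAS pain, "according to 80% power, 5% margin of error and 1.73 effect size", and settles on 10 patients per group.

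**The concern.** Baseline pain usually predicts later pain, and in a trial of 20 patients the arms can easily start apart. A comparison of week-2 scores alone carries that chance difference into the result and leaves explainable variance in the error term. The text does not use the word raw, but no change score is defined for analysis, so visit scores are the plain reading.

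The ANOVA does include baseline as one of its three time levels. However, it is conditional, and its interaction is a 2-df test over all visits. A significant result may come from week 6 alone, whereas the primary question concerns week 2. The reader would also be left with p-values and no adjusted treatment effect.

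**Working it through.** **Inputs.** From the documents: 10 per arm, 1:1 blocked allocation with no stratification by pain mentioned, significance level 0.05, effect size 1.73. Not in the documents, so assumed: baseline to follow-up correlation ρ of 0.3, 0.5 and 0.7; effects of 1.0 and 1.3 SD; two-sided testing.

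**The plan's own figure.** A two-sample t-test with d = 1.73 and 5 per group has power 0.802 at one-sided 0.05, so the stated 5 per group reproduces. A two-sided t-test needs 7 per group (power 0.844). The planned 10 per group gives 0.955 two-sided.

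**Chance imbalance.** In SD units, the difference in baseline means has SD √(2/10) = 0.447. So P(|difference| > 0.5 SD) = 2 × [1 − Φ(0.5/0.447)] = 0.264.

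The consequence can be large. With a 1.0 SD effect and ρ = 0.7, Mann-Whitney power is about 20% when the active arm starts about 0.5 SD worse and 84% when it starts about 0.5 SD better. ANCOVA power averaged over the two cases is 81%.

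**Variance.** Relative to the week-2 score, ANCOVA variance is 1 − ρ²: 0.91, 0.75 and 0.51 at the three correlations.

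**Power at week 2.** Simulation of 40,000 trials per scenario, normal scores, equal correlations between visits. The exact Mann-Whitney test at 10 per arm has size 4.3%.

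| Effect (raw SD) | Mann-Whitney | Raw t-test | ANCOVA, ρ = 0.3 / 0.5 / 0.7 |
|---|---|---|---|
| 1.0 | 51% | 56% | 57 / 66 / 82% |
| 1.3 | 74% | 78% | 80 / 87 / 96% |
| 1.73 | 94% | 96% | 96 / 98 / 99.8% |

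Part of each gap comes from using a t-type test instead of a rank test: 4 to 5 points at 1.0 and 1.3 SD, and 2 at 1.73. Adjustment alone, from unrounded figures, adds about 1, 10 and 26 points at 1.0 SD; 1, 8 and 18 at 1.3 SD; and 0.4, 2.6 and 4.3 at 1.73 SD.

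Rank ANCOVA at 1.3 SD has power 77%, 84% and 93%, so most of the gain at ρ = 0.5 and 0.7 remains within rank methods.

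**If 1.73 is in SDs of change.** The raw-score effect is then 1.73 × √(2(1 − ρ)) = 2.05, 1.73 and 1.34 SD. Mann-Whitney against ANCOVA becomes 98% against 99%, about 93% against 98%, and 77% against 97%.

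**Precision.** The mean 95% CI half-width is 0.93 SD on raw scores, against 0.91, 0.83 and 0.68 SD with ANCOVA.

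**The ANOVA interaction.** The test is F on 2 and (3 − 1)(20 − 2) = 36 df. At a 1.3 SD week-2 effect, its power is 68%, 83% and 97% if the effect is equal at week 6, and 55%, 70% and 91% if it halves. With no week-2 effect, 1.3 SD at week 6 and ρ = 0.5, it is significant in 83% of trials.

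**Bounded scale.** With VAS limited to 0–10, entry at 4 or above, and an assumed latent mean of 7 and SD of 1.7, the observed correlations fall to 0.27, 0.46 and 0.66. ANCOVA type I error is 5.0% to 5.2%. Power at 1.3 SD is 74%, 76% and 77% for Mann-Whitney against 80%, 87% and 96% for ANCOVA.

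**The case against.** The strongest reply is that the ANOVA already uses baseline, so setting ANCOVA against Mann-Whitney alone flatters ANCOVA. This has force. At 1.73 raw SD with an equal week-6 effect, the interaction has power 91%, 98% and over 99% at the three correlations. In the change-SD case at ρ = 0.7 it has about 98%, against 97% for ANCOVA. But at 1.73 SD its power falls to 81%, 92% and 99% if the effect halves by week 6. It is also conditional and cannot isolate week 2, whatever its power.

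A second reply is that the benefit rests on correlations the documents do not give, and that entry at VAS 4 or above lowers them. This stands in part. At ρ = 0.2 and 0.1, ANCOVA is slightly worse than the raw t-test: half-widths of 0.94 and 0.95 against 0.93 SD, and power at 1.0 SD of 55% and 54% against 56%. It still exceeds the 51% of the planned Mann-Whitney test.

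A third is that Mann-Whitney has ample power at the planned effect. That is true if 1.73 is a raw-score effect. But the figure comes from one earlier trial whose title in the reference list gives the primary motor cortex as its target, while this trial stimulates the left DLPFC. Smaller effects deserve planning.

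Finally, HADS, ACE-R, stiffness and FSS are named neither primary nor secondary, so adjustment there is a matter of consistency and has lower priority.

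**Conclusion.** The concern holds. The plan's rank test is valid and type I error is not inflated, so this is a weakness that should be corrected, not one that invalidates the trial. What is missing is one unconditional analysis that answers the week-2 question, uses the baseline already collected and yields an effect estimate.

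The size depends on the assumed correlation and effect. At correlations of 0.5 to 0.7 and effects of 1.0 to 1.3 SD, adjustment alone is worth about 8 to 26 points of power. At 0.3, or at a true raw-score effect of 1.73 SD, it is worth about 0.4 to 4 points. Separately from power, the omnibus interaction cannot stand in for a week-2 test.

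**What to change.** Name one primary analysis that does not depend on assumption tests: ANCOVA of week-2 VAS-pain on treatment and baseline VAS-pain, reporting the adjusted mean difference with its 95% CI, and state that the test is two-sided. Use the same model for week-6 VAS-pain, for stiffness, FIQ and FSS at weeks 2 and 6, and for HADS and ACE-R at week 6, each with its own baseline. Give rank-based ANCOVA or a permutation test of the same model as sensitivity analysis, and keep the repeated-measures ANOVA as supportive.

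The cost is one residual degree of freedom (20 − 3 = 17 instead of 20 − 2 = 18) and an assumption of linearity in baseline. No new data are needed. The Participants section already describes the enrolled sample ("range 29 to 64 years; 20 females"), so if the outcomes have been analysed, the ANCOVA must be labelled as chosen after the fact and shown beside the planned tests.

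### No analysis is named as primary for week-2 VAS-pain: a Mann-Whitney test and a conditional three-visit ANOVA both apply, and the ANOVA does not test week 2

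*Combined protocol and SAP*

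**What the plan says.** The section on outcome assessment and data collection fixes the endpoint and its time point: "Primary clinical outcome measure included VAS-pain (at the end of the 2nd week"). Later pain is a separate outcome: "secondary outcome measures included FIQ and VAS-pain scores at the end of the 6th week". No test is attached to either.

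The Statistical analysis section is the only analysis text, and it does not say which analysis is primary. It gives two between-group routes that reach VAS-pain:

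- **Mann-Whitney, no condition attached:** "Wilcoxon's signed-rank test and Mann-Whitney U-test were used to determine differences within and between the groups' baseline, 2nd or 6th week outcome parameters".
- **Repeated-measures ANOVA, conditional:** it applies "If the two groups met the assumptions in terms of pain, stiffness, FIQ, and FSS variables measured at three different times". The method is a two-way analysis, treatment by time, which the plan calls "variance analysis in repeated measurements".

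Shapiro-Wilk tests and Q-Q plots are mentioned, but no threshold is given and they are not tied to the choice of test. The section does not say whether the ANOVA replaces the Mann-Whitney test or adds to it, which ANOVA term counts, or whether a week-2 contrast follows.

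The Sample size section rests on change in VAS pain with an effect size of 1.73 and names no test. It raises the number to 10 per group with the words "Considering the statistical methods and the drop of patients from the study" and gives no drop-out rate.

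**The concern.** Two competent analysts following this text could report different p-values as the primary result. One would take the week-2 Mann-Whitney because it matches the endpoint. The other would take the ANOVA whenever its assumptions seem to hold and treat the rank test as a fallback.

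The second route does not answer the primary question. A treatment-by-time interaction over baseline, week 2 and week 6 asks whether the group difference varies across the three visits. The group main effect averages all three, baseline included. A difference that appears only at week 6, which is a declared secondary outcome, could therefore be presented as success on the week-2 primary. That would be a real effect under the wrong label, not a false treatment effect.

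If the better of the two p-values could be cited, the type I error for the primary outcome would also exceed 5%.

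**Working it through.** **Inputs from the documents.** 10 patients per arm, 1:1 allocation, VAS-pain at three visits, significance at 0.05, effect size 1.73.

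**Assumptions, because the documents give no values.** Normal data, SD 1, equal correlation ρ between visits of 0.3/0.5/0.7, two-sided tests. Triplets below follow that order of ρ.

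**1. The plan's own figure.** Five per group at 80% power and d = 1.73 comes out of a one-sided two-sample t-test (noncentrality 1.73·√(5/2) = 2.74 on 8 df, power 0.802). It also comes out of a two-sided paired t-test (1.73·√5 = 3.87 on 4 df, power 0.820). A two-sided two-sample t-test has power 0.670 at 5 per group and needs 7; at the planned 10 it has 0.955. So the planned size is not in doubt at d = 1.73, but the calculation does not reveal which test was meant as primary.

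**2. What the interaction responds to.** Let δ_t be the group difference in SD at visit t. The interaction is an F-test on 2 and 2·(20 − 2) = 36 df, with noncentrality

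λ = (n/2)·Σ(δ_t − mean δ)² / (1 − ρ), n = 10.

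- Week 6 only, δ = (0, 0, 1): the mean is 1/3, so the sum is 1/9 + 1/9 + 4/9 = 2/3.
- Weeks 2 and 6, δ = (0, 1, 1): the mean is 2/3, so the sum is 4/9 + 1/9 + 1/9 = 2/3.

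In both cases λ = 5·(2/3)/(1 − ρ) = 4.76/6.67/11.11. The interaction has the same power whether or not there is any effect at week 2.

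**3. Simulation.** 40,000 trials per scenario; exact Mann-Whitney at week 2, interaction F(2, 36), and ANCOVA of week-2 pain on baseline pain (20 − 3 = 17 df).

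| Effect, week 2 / week 6 (SD) | Interaction significant | Week-2 Mann-Whitney significant |
|---|---|---|
| 0 / 0 | 5.1/5.1/4.9% | 4.3/4.3/4.4% |
| 0 / 0.5 | 14.1/18.1/27.8% | – |
| 0 / 1.0 | 45.3/59.2/82.3% | 4.3/4.2/4.1% |
| 0.5 / 1.0 | 35.1/46.6/69.8% | 15.9/16.3/16.1% |

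- **No effect at any visit:** at least one of the two tests is significant in 8.5/8.7/8.9% of trials.
- **Disagreement on significance:** 40.0/41.2/44.6% at 1.0 SD at both visits; 13.2/7.8/6.7% at 1.73 SD at both visits.
- **Power of the week-2 tests, 1.0 SD:** ANCOVA 57.4/65.7/81.8%, Mann-Whitney 51.1/51.3/51.7%.
- **Power of the week-2 tests, 1.73 SD:** ANCOVA 95.8/98.3/99.9%, Mann-Whitney 93.4/93.8/93.4%.

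**4. Missing week-6 values.** A classical repeated-measures ANOVA drops a patient who has week-2 pain but no week-6 pain. With 1.0 SD at both visits and an assumed 2 per arm missing week 6, interaction power falls from 45.1/59.4/82.2% to 36.0/48.8/71.7%. A week-2 test loses nothing in that setting.

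**The case against.** The strongest reply is that the text nearly answers the question. The endpoint is one variable at one time point, and the Mann-Whitney is the only named between-group test that addresses it alone. On this view only a label is missing. It is the natural reading, but nothing in the text gives that test priority.

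A second reading takes the ANOVA if its assumptions hold and the Mann-Whitney otherwise. With Shapiro-Wilk p > 0.05 in all six group-by-visit cells as an assumed gate, null rejection is 4.9%/5.6%/5.0%, so that rule brings no material inflation. The 8.5–8.9% therefore applies only if either p-value may be cited. Even so, this reading lets a test that is not about week 2 decide the week-2 outcome.

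Three points on size stand:

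- A purely late effect is an extreme case, since 10 of the 14 sessions come before the week-2 assessment.
- At 1.73 SD the two routes mostly agree.
- Some disagreement at 1.0 SD simply reflects moderate power: ANCOVA and Mann-Whitney, both at week 2, disagree in 14%/22%/36% of trials there. Those two at least address the same question.

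The drop-out figures assume that losses fall after week 2; the plan gives neither timing nor rate. Finally, ANCOVA is not in the plan, and its power gain depends on the assumed correlations and normality for a bounded scale with an entry threshold of 4.

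**Conclusion.** The concern holds. The plan has a clearly stated primary endpoint without a designated test, and one of the two routes it offers cannot test that endpoint. That the interaction does not isolate week 2 follows from its form and needs no simulation.

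The practical size depends on the true effect. It is small if the effect is as large as 1.73 SD at both visits, and substantial for effects near 1.0 SD or effects that grow after week 2. The Objectives section itself cites meta-analyses that found no pain benefit over sham, so smaller effects cannot be set aside. The percentages rest on normal data, equal SDs and correlations of 0.3 to 0.7, none of which the documents give. This should be corrected, but it does not undermine the design or the planned sample size.

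**What to change.** State one between-group comparison of VAS-pain at week 2 as the sole primary analysis, two-sided at 0.05, whatever the distribution checks show, in all randomised patients with a week-2 value.

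- **Preferred:** ANCOVA of week-2 VAS-pain adjusted for baseline VAS-pain, reporting the adjusted difference with its 95% confidence interval, and the week-2 Mann-Whitney as sensitivity analysis.
- **Acceptable:** the plan's own week-2 Mann-Whitney as primary, at lower power. The section is written in the past tense, so if outcome data had been seen before the change, this is the safer choice because it adds no new test.
- **Either way:** label the treatment-by-time ANOVA, or a mixed model that keeps patients with a missing visit, as supportive only.

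The cost is one or two sentences and no new data. The freedom to choose the test after seeing the data is lost. ANCOVA spends one degree of freedom and relies on a roughly linear relation with baseline, which is why the rank test stays as a check.
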